PARTNERS HUMAN RESEARCH COMMITTEE
DETAILED PROTOCOL

PROTOCOL TITLE:

Ventilatory Support to Improve Exercise Training in High Level Spinal Cord Injury

10/17/2017

I. BACKGROUND AND SIGNIFICANCE

The cardioprotective effect of regular aerobic exercise in the general population is broadly accepted, but its importance for those with spinal cord injury (SCI) may be even greater.¹ Although regular aerobic exercise with sufficient intensity and duration can improve overall health, daily energy expenditure is low in those with SCI, due to lack of both motor function and options for accessible physical activity. To overcome this, we developed a unique form of exercise for those with SCI that specifically mirrors exercise performed by the able-bodied. Functional Electrical Stimulation Row Training (FESRT) couples volitional arm and electrically controlled leg exercise,² increasing the active muscle and resulting in the benefits of large muscle mass exercise. We have found improvements in peak aerobic capacity of up to 50% with FESRT in these patients.² However, despite the potential for enhancing aerobic capacity, those with high level lesions (C4 to T4) have the greatest denervation of pulmonary muscle and our preliminary work suggests this limits the aerobic capacity that can be achieved with FESRT. Despite the ability to train the denervated leg skeletal muscle via hybrid FES exercise, the inability to increase ventilation beyond limits set by high level SCI restricts aerobic capacity.

Respiratory restriction in SCI reduces inspiratory capacity in direct relation to lesion level,³ and those with high level injuries have the greatest compromise. As a result, the increase in ventilatory requirements with FES training results in an imbalance between ventilatory capacity and greater whole body skeletal muscle demand after FESRT. Hence, external ventilatory support could improve the ability to exercise train and hence enhance the adaptations to chronic exercise in high level SCI. In obstructive and restrictive pulmonary disorders, non-invasive ventilation (NIV) during exercise training can enhance exercise tolerance^{4,5} and improve gains in exercise capacity.^{6,7} Therefore, we hypothesize that the use of NIV during FESRT will reduce ventilatory limits to exercise, leading to greater exercise tolerance and increased aerobic capacity in high level SCI.

We have access to a large (N>70) and unique population of individuals with SCI who have been enrolled in FESRT for at least 6 months. Roughly half have high level SCI between C4 and T4.

II. SPECIFIC AIMS

Aim 1: To determine the magnitude of improvement in aerobic capacity after 3 months of FESRT+NIV compared to FESRT+shamNIV in high level spinal cord injury.

Aim 2: To examine the relationship among gains in ventilation and increases in the determinants of aerobic capacity - maximal cardiac output and arterio-venous oxygen difference after 3 months of FESRT+NIV in high level spinal cord injury.

Aim 3: To examine the acute effect of NIV on FES-row VO₂max in subjects with both high and low level SCI.

III. SUBJECT SELECTION

FES-Row-Training Group

Thirty individuals with high level SCI who have FES-row trained for at least 6 months will be randomized to (continued) FESRT for 3 months with either NIV or sham NIV. Patients will be medically stable and inclusion criteria are SCI at neurological level \geq T4 with American Spinal Injury Association grade A or B or C, aged \geq 18 years of age. Before and after training, we will assess maximal aerobic capacity, ventilation, cardiac output, and arterio-venous oxygen difference. Based on our current data, we hypothesize that only those randomized to NIV will experience further increases in aerobic capacity and that these increases will relate to increased cardiac output and arterio-venous oxygen difference. This project will determine the feasibility and effectiveness of this approach to exercise and will lay the groundwork for a larger study of the impact of FESRT+NIV to improve health and function in those with high level SCI.

FES-Row-Exercise Testing Only Group (Cross-Sectional)

Fifteen individuals with SCI who have FES-row trained for >6 months will perform FES-VO₂max row tests on separate days with and without the use of NIV to determine maximal aerobic capacity and ventilation. Patients will be medically stable and inclusion criteria are SCI at neurological level C5-T12 with American Spinal Injury Association grade A or B or C, aged \geq 18 years of age. In our first four subjects, we have observed an increase in maximal aerobic capacity at baseline with NIV assisted increases in ventilation. This was unexpected; we hypothesized that we would increase ventilation during the test at baseline, but that aerobic capacity would not be higher because it would be proportional to the voluntary (unassisted) maximal ventilation. However, this indicates that maximal aerobic capacity in these individuals exceeds maximal voluntary ventilation. It will be important to determine the consistency of this response and at what level of injury it is not observed. We have a large population of potential subjects who have completed six months of FES-row exercise training across a range of SCI level (C5-T12). Hence, we can determine the consistency of the effect and the dependence of the effect on SCI level. (E.g., We could obtain data from those with high level SCI who do not want to enroll in 3 months of training with NIV or sham NIV.)

Exclusion criteria for all subjects are blood pressure >140/90 mmHg, significant arrhythmias, coronary disease, chronic respiratory disease, diabetes, renal disease, cancer, epilepsy, current grade 2 or greater pressure ulcers at relevant contact sites, other neurological disease, peripheral nerve compressions or rotator cuff tears that limit the ability to row, and history of bleeding disorder.

Note: Any changes in cardioactive medications during the exercise testing or training protocols will be evaluated by the Principal Investigator and could lead to removal from the study.

IV. SUBJECT ENROLLMENT

Research study staff will obtain volunteer consent in accordance with guidelines established by the Institutional Review Board during the first visit to the Laboratory. Participants will be sent the consent form at least 48 hours in advance so they have ample time to read and ask questions. Participants are encouraged to ask questions and are reminded that participation is strictly voluntary and will not affect their current or future care at Spaulding Rehabilitation Hospital or any of its affiliates.

V. STUDY PROCEDURES

Once recruited for the study the volunteer will visit the laboratory for a health screening session to further determine eligibility. This one-hour session will include obtaining informed consent, detailed health history, height and weight measurements, resting blood pressure, resting heart rate and NIV-device familiarization trial.

Subjects may also be asked to provide additional medical records or may need further testing to determine their eligibility and the safety of their participation in this program which includes regular vigorous exercise. These additional tests may or may not be covered by insurance. The subjects will be responsible for obtaining any additional testing and providing the program with medical records or results.

FES-Row-Training Groups and Training Protocols

NIV support. Participants randomized to NIV will perform row training while receiving bi-level positive airway pressure ventilation applied through a full-face mask (Phillips Respironics, Murrysville, USA). The ventilator will be set in a spontaneous mode with a ramp to reach a minimal pressure of 12 cmH₂O during inspiration and 4 cmH₂O during expiration. A minimal duration for inspiration time may also be imposed if the patient desynchronizes with ventilator support. Parameters will then be adapted according to participant's comfort and ventilatory requirement during exercise.

Sham-NIV. In the sham group, similar conditions will be used but the ventilator will be applied with maximal pressure support of 5 cmH₂O of inspiratory pressure and 2-4 cmH₂O of positive end-expiratory pressure to overcome the resistance of the breathing circuit.

Subjects in the NIV support group and Sham-NIV group will be blinded to which group they are in and how much NIV support they are receiving.

FES-Row Training. The FES row system will optimize the contribution of the pre-trained muscle components of quadriceps and hamstrings. To maintain the proper training stimulus at the same relative intensity, a maximum FES-rowing test will be performed at baseline for intensity to be determined. The goal is for each volunteer to achieve an exercise intensity of 75-85% maintained for at least 30 minutes performed three times each week. Measurements of force produced at the foot and handle during FES-row training sessions will also be used to monitor training and possibly improve rowing technique. Subjects exercise programs will be tailored specifically to their fitness level but should progress quickly to the prescribed intensity as all subjects

There is no limit or specific requirement for training sessions that must be attended to continue participating in this protocol. Subjects will be encouraged by study staff to attend three training sessions per week. Un-reported missed training session will be followed up with a phone call to document why the training session was missed and to encourage prompt return to training sessions as soon as possible.

Strength Training during FES-RT

As subjects will already have been participating in FES-row training they will also be given the opportunity to continue or start the FES-leg strength training at home concurrently on non FES-rowing days (~3 days/week, 30-60 minutes/session). This will be possible after the subjects have demonstrated the knowledge and ability of proper use of the stimulation unit for home use. This will be

closely monitored, as they will also be FES-rowing three times per week at Spaulding Cambridge.

Study Assessments

FES-Row Training Group

All Assessments will be performed at baseline and after three months of FES-row training. There will be 2 separate FES-VO₂max row tests, 2 separate Cardiac Output row tests and 1 Pulmonary Function test done at each time point (done at least 48-hours apart). Both NIV Support and Sham-NIV groups will perform tests with and without use of the NIV-machine.

FES-Row Exercise Testing Only Group

Subjects will perform FES-VO₂max row tests on separate days with and without the use of NIV to determine maximal aerobic capacity and ventilation. Both FES-VO₂max Row tests will be performed at least 48-hours apart

Measurements and Testing Protocols:

FES-Row-VO₂max Testing

Individuals will refrain from eating for 2 hours prior, from caffeine and alcohol for 24 hours prior, and from vigorous physical activity for 48 hours prior to testing. Aerobic power will be determined from online computer-assisted open circuit spirometry and expired gas analysis will be performed continuously throughout the test with the Innocor rebreathing system (Innovision, Odense, Denmark, see details below). A heart rate monitor (Suunto, [name]) will be used throughout the tests. The baseline graded FES row test protocol will be based on each individual's initial FES row response, and 1- to 2-minute workloads will be selected to achieve test protocols of 8 to 12 minutes of incremental exercise. The same protocol will be used for the 3-month posttest unless the initial workload has become too low to allow proper FES rowing technique. In this case, the initial workload will be the second workload from the pretest. To ensure attainment of peak exercise capacity, at least 3 of the following criteria must be met: 85% of age predicted maximal heart rate ($220 - \text{age}$), respiratory exchange ratio >1.1 at end exercise, plateau in oxygen consumption despite increasing workload, blood lactate level (Lactate Plus, Nova Biomedical, Waltham MA) of 8 mM or above, rating of perceived exertion of at least 17 on the Borg scale of 6 to 20, and precipitous decline in power $>20\text{W}$ during maximal leg stimulation. Peak oxygen consumption will be defined as the highest value achieved over 30 seconds.

Immediately after FES-rowing has stopped at the end of the VO₂max test, subjects will have a finger tip pricked with a safety lancet in order to get a drop of blood that will be used to measure peak lactate levels in whole blood. Peak lactate levels will be used to evaluate exercise intensity as well as to monitor training status.

Cardiac Output Row Testing

Individuals will refrain from eating for 2 hours prior, from caffeine and alcohol for 24 hours prior, and from vigorous physical activity for 48 hours prior to testing. Cardiac output will be measured at rest and during a three to six minute FES-row steady state exercise bout at an intensity of 80% of peak heart rate. Cardiac Output is measured using the inert gas re-breathing method (Innocor, Innovision, Odense, Denmark), a previously validated non-invasive method for rest and exercise measures. Notably, inert gas re-breathing measurements of cardiac output do not require steady state conditions and hence can be

obtained during graded tests. An oxygen-enriched mixture of an inert soluble gas (0.5% nitrous oxide) and an inert insoluble gas (0.1% sulphur-hexafluoride) are used to indirectly assess pulmonary blood flow and lung volume, respectively. In the absence of pulmonary shunt, cardiac output = pulmonary blood flow. Arteriovenous oxygen difference will be derived by applying the Fick principle: arteriovenous oxygen difference = oxygen consumption / cardiac output. Subjects will do 2 re-breathing maneuvers at rest and 2 re-breathing maneuvers once they have achieved target heart rate.

Pulmonary Function Tests

Spirometry will be used to measure lung function, specifically the measurement of the amount (volume) and/or speed (flow) of air that can be inhaled and exhaled. Specifically, Forced Volume Vital Capacity (FVC) and Maximum Voluntary Ventilation (MVV) tests will be administered.

Regional Cerebral Blood Flow

A Near-Infrared Spectroscopy (NIRS; PortaLite, Artinis Medical Systems) probe placed on the forehead contralateral to the dominant hand will be used to measure blood oxygenation during maximal exercise testing. NIRS-derived blood oxygenation levels will be used as a measure of cerebral blood flow at the prefrontal cortex.

VI. BIOSTATISTICAL ANALYSIS

This pilot project will employ a simple and straightforward statistical approach to compare changes within and between groups. Statistical significance will be set at 0.05, and power at 80%. Normality and equality of variance will be assessed using tests of skewness and kurtosis. Within and between group (FESRT+NIV vs. FESRT+shamNIV) comparison of changes will be made using a general linear model accounting for potential baseline differences and the intervention effect. Correlations between ventilation, aerobic capacity, and hemodynamics variables (cardiac output and arteriovenous oxygen difference) will be assessed by Pearson's or Spearman's coefficient depending on the normality of the variables. If significant relations are found, appropriate regression analyses will be employed.

VII. RISKS AND DISCOMFORTS

Moderate risks are associated with exercise testing and exercise training. Some discomfort and feeling of fatigue will be experienced during these tests. There are other risks associated with these tests including abnormal blood pressure responses, fainting, irregular, fast or slow heart rhythm, and in rare instances, heart attack, stroke, or death. Wearing the face-mask during the VO₂max testing and FES-row training may cause feelings of claustrophobia. Exercise training may induce some muscle or joint discomfort when beginning an exercise program and could result in tendonitis and/or musculoskeletal overuse injuries over time. Subjects may feel lightheaded or short of breath during use of the NIV machine and during the cardiac output measurement. The electrical stimulation unit can cause tingling, pins and needles sensations on the skin, skin irritation, increased muscle spasticity and autonomic dysreflexia (signs include: headache, nausea, rise in blood pressure, sweating, and goosebumps). There is some discomfort with the lancet used on the finger for lactate measurement and there is a small possibility of swelling and bruising at the site(s), there is also a slight chance that individuals become dizzy and even faint. Subjects may feel lightheaded or short of breath during the pulmonary function tests, there is also a slight chance that individuals become dizzy and even faint.

VIII. POTENTIAL BENEFITS

Volunteers will have the opportunity to participate in a supervised exercise program, which may

improve their overall cardiovascular fitness and endurance during activities of daily living as well as decrease risk of chronic disease.

IX. MONITORING AND QUALITY ASSURANCE

The research coordinator will be responsible for monitoring the completeness of all data and source documents. The Principal Investigator will monitor the informed consent procedures in accordance with the Informed Consent Compliance Checklist of Partners HealthCare Systems HRQIP. The subject's data/protocol adherence will be monitored by the research coordinator at each step in the study including. Checklists and note pages are used to note any deviations or omissions from the protocols. The Cardiovascular Research Laboratory Medical Emergency Safety Plan will be followed in the case of an adverse medical event. Any clinical/health related issues would be immediately presented to the subject (i.e. abnormal EKG, etc) to determine appropriate notification (ie. current physician or appropriate specialist)

At each visit, study staff will prompt the participant to report any occurrences of health changes or problems. Any serious or non-serious adverse event will be recorded in the participant's study folder and adverse event log and reviewed by the PI. Serious and non-serious adverse events will also be reported to the Human Research Committee in accordance with Human Research Committee reporting guidelines, following the timeframes specified by the Partners Investigator's Guidelines. In case of a serious adverse event appropriate diagnostic and therapeutic measures will be taken, as determined by the investigator.

REFERENCE LIST

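### Aim 2 correlates gains after FESRT+NIV with no sham comparison, so it cannot attribute a ventilation link to NIV; for VO2 and a-v O2 difference, ventilation may also be part of the outcome

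*Combined protocol and SAP*

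**What the plan says.** Section II words Aim 2 as "To examine the relationship among gains in ventilation and increases in the determinants of aerobic capacity", and continues: "maximal cardiac output and arterio-venous oxygen difference after 3 months of FESRT+NIV in high level spinal cord injury". Aim 1 sets NIV against sham; Aim 2 names only the NIV condition.

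Section VI gives the analysis: "Correlations between ventilation, aerobic capacity, and hemodynamics variables (cardiac output and arteriovenous oxygen difference) will be assessed by Pearson's or Spearman's coefficient", the choice depending on normality. It continues: "If significant relations are found, appropriate regression analyses will be employed". This adds aerobic capacity to Aim 2's variables and does not say which arm or arms are used. The baseline-adjusted linear model in the same section is stated for changes within and between groups, not for the correlations.

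Three measurement statements in Section V matter:

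- VO2max testing: "Aerobic power will be determined from online computer-assisted open circuit spirometry and expired gas analysis".
- Cardiac output testing: "Cardiac Output is measured using the inert gas re-breathing method", in a separate steady-state bout at 80% of peak heart rate.
- a-v O2 difference is derived: "arteriovenous oxygen difference = oxygen consumption / cardiac output".

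Under Study Assessments, both arms do the same tests at baseline and three months, with and without the machine. FVC and MVV come from a separate pulmonary function test. The plan does not say which of these supplies the ventilation gain.

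**The concern.** Section I hypothesises that NIV relieves a ventilatory limit and so raises aerobic capacity. Section III adds that gains are expected only under NIV and will relate to cardiac output and a-v O2 difference. Aim 2 is the part of the plan that speaks to this mechanism, but as worded it has no treatment contrast. Someone who rows harder, or is fitter, at three months will tend to breathe more, pump more blood and consume more oxygen whatever NIV did. The same pattern could appear under sham, where the same data are collected and Aim 2 does not use them.

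For two of the outcomes there is a second source of correlation. VO2 by open-circuit spirometry is ventilation multiplied by the fraction of oxygen extracted, so a ventilation gain and a VO2 gain from one test share a term. The a-v O2 difference inherits that term through VO2.

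At stake is what Aim 2 can add to the planning of the larger study that Section III foresees.

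**Working it through.** **The plan's own figures.** Section VI gives alpha 0.05 and 80% power, and Section III gives 30 randomised. No effect size, SD or target correlation connects them, and none is given for Aim 2, so there is no figure to reproduce. I assume 1:1 allocation (15 per arm) and two-sided tests.

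**Step 1: what n = 15 can detect.** The critical value is |r| = t/√(n − 2 + t²). With t = 2.160 on 13 df, |r| = 2.160/√(13 + 4.67) = 0.514. For 80% power by Fisher's z, r = tanh(2.80/√12) = 0.67.

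**Step 2: a one-arm correlation carries no treatment contrast.** If NIV adds the same amount to everyone's log ventilation gain, the arm's mean moves and every deviation from it stays the same, so r is unchanged. Simulation agrees: the ventilation-VO2 correlation reached p < 0.05 in 89% of trials with and without such a shift (SD ratio 1, independent components, as in Step 4).

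**Step 3: shared effort or fitness alone.** With no arithmetic link, a true correlation of 0.3, 0.5 or 0.7 reaches p < 0.05 in 19%, 50% or 88% of trials at n = 15. This is the only route for cardiac output; without shared effort, the rate for ventilation against cardiac output is the nominal 5%.

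**Step 4: the arithmetic link for VO2.** Write Δln VO2 = Δln VE + Δln F, where VE is ventilation and F the extracted fraction. Let k = SD(Δln F)/SD(Δln VE) and ρ be their correlation; both are assumptions. Then

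r(VE, VO2) = (1 + kρ)/√(1 + k² + 2kρ).

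For example, k = 1 and ρ = 0 give 1/√2 = 0.71. The table shows the built-in r and, in brackets, how often it reaches p < 0.05 at n = 15 (100,000 simulated trials per cell, no NIV effect).

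| k | ρ = 0 | ρ = −0.5 | ρ = −0.8 |
|---|---|---|---|
| 0.5 | 0.89 (99.9%) | 0.87 (99.7%) | 0.89 (99.9%) |
| 1 | 0.71 (89%) | 0.50 (50%) | 0.32 (21%) |
| 1.5 | 0.55 (61%) | 0.19 (10%) | −0.22 (12%) |

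The percentages are power to detect a correlation that is really present under the assumptions. They are not false-positive rates.

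**Step 5: a-v O2 difference.** Δln(a-v) = Δln VO2 − Δln CO. Assume SD(Δln CO) = SD(Δln VE) and cardiac output independent of ventilation. Then r(VE, a-v) = (1 + kρ)/√(2 + k² + 2kρ). At k = 1 and ρ = 0 this is 1/√3 = 0.58 (significant in 66% of trials); over the same grid the rate runs from 8% to 83%. If cardiac output correlates 0.5 with ventilation, the k = 1, ρ = 0 figure falls to 0.35 (26%). All of this requires that the VO2 in the ratio and the ventilation gain share a test or move together.

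**Step 6: comparing arms.** With the k = 1, ρ = 0 link equal in both arms and no NIV effect, the arm-by-ventilation-gain interaction was significant in 4.9% of 20,000 simulated trials and the randomised contrast in VO2 gain in 5.0%. A link common to both arms therefore does not disturb either comparison.

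**Step 7: power for an arm difference.** As a guide, use two correlations at 15 per arm. The SE of the difference in Fisher's z is √(1/12 + 1/12) = 0.408, so 80% power needs 2.80 × 0.408 = 1.14. If sham r = 0, NIV r must be tanh(1.14) = 0.82. If sham r = 0.5 (z = 0.549), NIV r must be tanh(1.69) = 0.93.

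**The case against.** The strongest reply is that nothing in the plan treats this correlation as a test of NIV. Aim 2 sets out to examine a relationship, Section VI calls the study a pilot, a significant correlation leads only to regression, and the NIV effect is Aim 1's randomised comparison. That stands. A reader might infer that a significant Aim 2 result will be taken as proof that NIV works; no section says so.

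A reader might also take the table as false-positive rates against 5%. They are not. The planned test is of r = 0, and where the assumed r is 0.71, rejecting is correct. The difficulty is what a non-zero r means.

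The arithmetic argument is also narrower than it looks. Aim 2 itself names cardiac output and a-v O2 difference; aerobic capacity enters only in Section VI. Cardiac output comes from rebreathing in a separate session, the sessions being spaced by 48 hours or more. If the ventilation gain is MVV, or comes from a different session from the VO2 used, the shared term disappears or weakens. These limits stand, but the plan leaves the choice of ventilation measure open, so the linked choice is not excluded.

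Some protection exists. The VO2max test requires three of six peak criteria and repeats the baseline protocol unless the starting workload has become too low, which limits variation in effort. The linear model for changes plausibly covers the between-arm difference in ventilation gain. Neither puts a sham comparison into the correlations.

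Finally, Section VI names no arm, so pooling both arms is possible. Pooling without an arm term would not help: a difference between arm means in both variables would itself contribute to r.

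**Conclusion.** The point holds in limited form. As worded, Aim 2 and its Section VI correlations contain no treatment contrast, so they cannot say whether a link between ventilation gain and outcome gain is due to NIV. This rests on the wording and needs no assumed variance.

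The arithmetic link is a conditional addition. It applies to VO2, and to a-v O2 difference derived from it, when ventilation comes from the same test. It does not apply to rebreathing cardiac output or to MVV. Its size in this trial cannot be fixed: with assumed SD ratios of 0.5 to 1.5 and correlations of 0 to −0.8, the built-in ventilation-VO2 correlation runs from −0.22 to 0.89.

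It is tempting to conclude that MVV should replace exercise ventilation as the main measure. The documents do not support going that far: MVV is itself a voluntary maximal manoeuvre, so effort can still confound it, and it is not ventilation during rowing. Aim 1 is unaffected. The change is worth making because the sham data are already being collected.

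**What to change.** In Section VI:

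- Analyse Aim 2 in both randomised arms (all 30). Regress each outcome gain on ventilation gain, with arm, the outcome's baseline value and an arm-by-ventilation-gain interaction.
- Report the between-arm difference in ventilation gain, and the same correlations in the sham arm beside those in the NIV arm.
- State which test supplies the ventilation gain, including whether the machine was in use, and which VO2 enters the a-v O2 difference. Use change in MVV as a sensitivity analysis.
- Label Aim 2 exploratory and the within-NIV correlation descriptive. Rest any claim of an NIV effect on the randomised Aim 1 comparison.
- Reconcile Aim 2's reference to maximal cardiac output with the steady-state bout at 80% of peak heart rate in Section V.

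The cost is wording and one extra model per outcome; no new data are needed. Power for the interaction will be low at about 15 per arm. A non-significant interaction would not show that the slopes are equal, and equal slopes would not rule out NIV acting through ventilation. Ventilation gain is measured after randomisation, so its association with outcome remains observational even with arm in the model.

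### After screening, the protocol schedules no blood pressure reading at any exercise test or training session, although it names pressure disturbances among the risks

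*Combined protocol and SAP*

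**What the plan says.** - **Entry.** Section III sets 140/90 mmHg as the upper limit for all participants. The opening of Section V puts the only scheduled blood pressure measurement at the screening visit, where the list includes "resting blood pressure, resting heart rate and NIV-device familiarization trial".
- **Who is exposed.** On the randomized participants, Section III states: "Thirty individuals with high level SCI who have FES-row trained for at least 6 months will be randomized to (continued) FESRT for 3 months". Their lesions are at T4 or above. A further 15 participants, with lesions from C5 to T12, do two VO₂max row tests each.
- **Training sessions** (Section V, FES-Row Training): "Measurements of force produced at the foot and handle during FES-row training sessions will also be used to monitor training".
- **Assessments** (Section V, Study Assessments): at baseline and at three months the training group has two VO₂max row tests, plus "2 separate Cardiac Output row tests and 1 Pulmonary Function test done at each time point (done at least 48-hours apart".
- **VO₂max tests** (Section V): expired gas, heart rate, perceived exertion and power are followed, and afterwards "subjects will have a finger tip pricked with a safety lancet in order to get a drop of blood" for lactate.
- **Cardiac output tests** (Section V): "Cardiac output will be measured at rest and during a three to six minute FES-row steady state exercise bout", by inert gas re-breathing.
- **Cerebral measurement** (Section V): NIRS on the forehead during maximal testing records blood oxygenation, not pressure.
- **Risks** (Section VII): for the exercise tests, "abnormal blood pressure responses, fainting, irregular, fast or slow heart rhythm, and in rare instances, heart attack, stroke, or death"; for the stimulation unit, among other effects, "autonomic dysreflexia (signs include: headache, nausea, rise in blood pressure, sweating, and goosebumps".
- **Safety handling** (Section IX): staff ask about health changes at every visit, events are logged and reviewed by the Principal Investigator, and the laboratory's Medical Emergency Safety Plan applies once an adverse medical event has occurred.

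**The concern.** The protocol uses blood pressure to decide who may enter, and it names pressure disturbance as a hazard of the exercise and of the stimulation. It then schedules no pressure reading at any of the sessions where that hazard arises. Of the five dysreflexia signs in Section VII, four (headache, nausea, sweating, goosebumps) can be seen by staff or reported by the participant. The fifth, a rise in pressure, has to be measured.

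The safeguards in Section IX start from a sign or a report, so nothing listed in the protocol would pick up a pressure rise that produces neither. Staff would also have no same-day resting value to compare with when a sign does appear. Two features of the sessions plausibly make signs less dependable: participants wear a face mask while rowing, which may hinder speech, and sweating is expected during vigorous exercise.

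What is at stake is participant safety. The treatment comparison is not.

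**Working it through.** **Step 1. Where blood pressure appears.** It occurs in three places: the exclusion limit (Section III), the screening visit (Section V) and the risk text (Section VII). Set against the scheduled procedures:

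| Occasion | What is listed | Blood pressure listed? |
|---|---|---|
| Screening | history, height, weight, resting pressure, resting heart rate, NIV familiarization | yes |
| Training session | foot and handle force | no |
| VO₂max test | expired gas, heart rate, exertion rating, power, lactate, NIRS | no |
| Cardiac output test | re-breathing at rest and at target heart rate | no |
| Optional home stimulation | close monitoring, no measurement named | no |

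The screening entry is one scheduled occasion. The protocol does not say how many readings are taken there.

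**Step 2. Stimulated rows without a scheduled reading.** The plan gives no such figure, so there is none to reproduce. Inputs from Sections III and V: 30 randomized, 15 testing-only, two VO₂max and two cardiac output tests at each of two time points for the randomized, two VO₂max tests for the testing-only group, and three sessions a week for three months. Assumptions: 13 weeks; the baseline intensity test is one of the VO₂max tests; the 15 are separate from the 30.

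- VO₂max tests: 30 × 2 × 2 + 15 × 2 = 120 + 30 = 150
- Cardiac output tests: 30 × 2 × 2 = 120
- Training sessions: 30 × 3 × 13 = 1,170
- Total: 150 + 120 + 1,170 = 1,440

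Section V sets no attendance requirement. At an illustrative half attendance the total is 150 + 120 + 585 = 855. With 12 weeks instead of 13, full attendance gives 30 × 3 × 12 = 1,080 sessions and 150 + 120 + 1,080 = 1,350 rows. Screening supplies 30 + 15 = 45 scheduled occasions. Home stimulation is not in these counts.

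**Step 3. Readings and staff time, at two readings per row.**

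- Per randomized participant: (8 tests + 39 sessions) × 2 = 94; at half attendance (8 + 19.5) × 2 = 55; with 12 weeks (8 + 36) × 2 = 88
- Per testing-only participant: 2 × 2 = 4
- In total: 1,440 × 2 = 2,880; at half attendance 855 × 2 = 1,710; with 12 weeks 1,350 × 2 = 2,700
- At an assumed 1 minute each: 2,880 / 60 = 48 hours, or 1,710 / 60 = 28.5 hours at half attendance
- At an assumed 2 minutes each: 96 hours, or 57 hours at half attendance

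Repeat readings and readings prompted by a sign come on top.

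**The case against.** The strongest reply is that silence in Section V is weak evidence about practice. That section mainly lists outcome and training measurements. Section IX gives an abnormal EKG as an example of a finding to be raised with the participant, yet Section V schedules no EKG, so it is probably not a full account of clinical monitoring. The emergency plan is cited but not reproduced. This stands: a reader might infer that pressure goes unwatched during the trial, and the documents do not support that. What they do show is that no reading is scheduled. The emergency plan does not replace one, because it applies only after an event.

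Other safeguards deserve full weight. Participants are medically stable and have at least six months of FES rowing behind them. Besides the pressure limit, Section III excludes significant arrhythmias and coronary disease and has the Principal Investigator evaluate changes in cardioactive medication. Section V allows further testing on safety grounds, and the program is supervised. These lower the risk at entry or act on signs and reports; none measures pressure at a session.

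Three objections to adding readings also hold in part.

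- **Interrupting exercise for sweating would do harm.** It is an ordinary response to maximal effort, and stopping an 8 to 12 minute graded test for it would lose VO₂max data that a trial of 30 can ill spare. Any rule must leave out sweating alone during exercise.
- **A reading without an action limit is of little use.** The protocol's 140/90 mmHg can serve.
- **Readings before and after rowing close the gap only partly.** A rise that settles before the cuff is read is still missed, and home stimulation, at about three days a week, is not covered.

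**Conclusion.** The point holds as a statement about what the protocol schedules: one blood pressure occasion per participant, at screening, and none at the roughly 1,440 stimulated rows that follow at full attendance (855 at half; 1,350 at full attendance if three months means 12 weeks). That much is certain from the text. The counts rest on the assumptions listed in the working.

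It is a cheap safety improvement, to be considered, and should not be read as more. Three stronger readings are tempting. A reader might take the 1,440 rows as a measure of harm, but the documents give no rate of dysreflexia or of symptomless rises, so no number of missed events can be stated. A reader might infer that NIV raises pressure, or that the gap biases the comparison; both arms have the same exercise and stimulation, and Aims 1 to 3 do not depend on blood pressure. A reader might also conclude that staff could not recognize dysreflexia, but four of its five listed signs need no instrument.

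**What to change.** Add to Section V, for every VO₂max test, cardiac output test and supervised training session:

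> Seated blood pressure will be taken by arm cuff just before stimulation starts and within about 2 minutes after rowing stops. At VO₂max tests the cuff goes on the arm not used for the lactate sample; at cardiac output tests the first reading precedes the resting re-breathing. A pre-exercise reading above 140/90 mmHg is repeated and referred to the Principal Investigator before the row starts. A post-row reading that stays above 140/90 mmHg is repeated until it settles, and referred if it does not. Rowing and stimulation are stopped and a reading is taken for headache, nausea or goosebumps, but not for sweating alone during exercise. Dysreflexia episodes are entered in the adverse event log.

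If an existing laboratory procedure already covers this, citing it in Section V would serve as well.

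**Cost.** A short amendment and two form fields. The screening visit already requires blood pressure equipment, and staff are present at these sessions. The time is the 48 to 96 hours derived above at full attendance (28.5 to 57 at half), plus repeat and sign-prompted readings. Some tests or sessions will be delayed or stopped, with possible loss of a VO₂max or cardiac output measurement. Rises that settle before the reading, and home stimulation, remain uncovered.
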